## **8.5 Rationale and Justification for the Booster Phase.**

Following the successful completion of the Part A primary analysis (Day 36), the high dose was found to be the optimal dose as defined in the primary objective of the study. Based on the assessed comparable safety and superior immunogenicity results at Day 36, the high dose has been selected for further clinical development. Valneva has decided to extend the VAL2001-201 study, by investigating the effects of a Booster dose at 8-9 months after completion of the primary immunization schedule with VLA2001. The booster dose will be offered to all participants who do not meet an exclusion criteria regardless of their initial response to the primary immunization schedule in the different dose groups. Hence, the effect of a booster dose will be studied in a population with different levels of pre-existing antibody levels against SARS-CoV-2.

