## **14. ASSESSMENT OF IMMUNOGENICITY**

All serum samples obtained for the determination of neutralizing antibodies and IgG antibodies against SARS-CoV-2 will be handled according to the procedures supplied to each investigative site for the preparation, storage and shipment of samples (refer to Laboratory Manual). Immunogenicity samples will be collected from all Participants at the time points indicated in section 22.2 and 22.3. Each clinical study site will be responsible for the separation of serum from whole blood samples and the safe and controlled storage of serum samples prior to shipment to the central laboratory.

Immunogenicity sample (10ml) will be drawn for SARS-CoV-2-specific neutralizing antibody titre evaluation and ELISA antibody titre evaluation.

Serum samples to measure SARS-CoV-2 neutralizing antibody levels will be collected from Participants on Day 1 (prior vaccination), Day 8, Day 22 (prior vaccination), Day 36, Day 106 and Day 208. An authorized laboratory will measure neutralizing antibodies to SARS-CoV-2 using wild-type virus neutralizing assay. In addition to the functional assays, samples will be analysed for IgG against SARS-CoV-2 by ELISA.

The cell-mediated immune response (T-cell response) will be assessed on Day 1, Day 36 and Day 208 by characterizing PBMCs; methods may include T-cell ELISpot assays to SARS-CoV-2 antigens.

Booster Phase:

During the Booster Phase, a blood sample (10 ml) will be collected at Visit 7 (before vaccination), Visit 8 and Visit 9, to measure SARS-CoV-2-specific neutralizing antibody titre and ELISA antibody titre.

Similarly, cell-mediated immune response (T-cell response) will be assessed by characterizing PBMCs at Visit 7 and Visit 8.

More details about the Booster Phase assessments can be found in section 22.3.

At the end of the study, results of immunogenicity assessments will be provided to the Investigator.

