#### **16.5 Planned Data Analysis of the Study**

The following data analyses will be performed:

- Part A includes safety and immunogenicity data after all Participants have completed Visit 4 (Day 36).
- Part B includes safety and immunogenicity data after all Participants have completed Visit 6 (Day 208).
- An additional data analysis will be performed during part B after all Participants have completed Visit 5 (Day 106)
- Part C includes Visits 7 to 10. An analysis of Part C will be done when all participants have completed visit 9.
- Final analysis will be done when all participants have completed the last visit (visit 10)

Individual study parts will be analysed sequentially.

Part A analysis will be performed once the last Participant has completed Day 36 (Visit 4) and will comprise the primary immunogenicity and safety endpoints; the study will be unblinded at this time. Part B analysis will be performed once the last Participant has completed Day 208 (Visit 6).

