### 22.3 Schedule of Study Procedures and Assessments for the Booster Phase

The investigator may schedule visits (unplanned visits in addition to those listed in the table, in order to conduct evaluations or assessments required to protect the well-being of the participant

Procedures/Assessments	Visit 6 Day 208 M7 (+/- 14d)	Visit 7 i Planned for mid-end September 2021 for all participants (+/- 14d)	Visit 8 14 days after booster vaccination (Visit7)  (+/- 2d)	Visit 9 28 days after booster vaccination (Visit7)  (+/- 7d)	Visit 10 Safety follow- up call 6 months after booster vaccination (Visit 7)  (+/- 14d)	Unplanned COVID- 19 Illness Visit	Ad hoc Safety Call in case of e- Diary entry (Grade 3 AE or SAE)	Visit ET
Informed consent	X							
Inclusion/Exclusion criteria check	X	X						
Delay criteria check		X						
Symptom-driven physical examination a	X	X	X	X		X		X
Prior/Concomitant medications	X	X	X	X	X	X	X	X
Vital signs b	X	X						
Urine Pregnancy test c		X						
Safety labs d [10 mL]	X	X	X	X		X		X
Immunogenicity sample e [10 mL]	X	X	X	X		X		X
Blood for PBMC Isolation f [50 mL]	X	X	X					
Saliva Sample k	X							
VACCINATION		X						
Electronic Participant Diary		E	R	R			R	R
AE/AESI/SAE Assessment	X	X	X	X	X	X	X	X

(S)AE=(serious) adverse event; AESI=adverse event of special interest; PBMC=peripheral blood mononuclear cells; R=review

- a **A symptom-driven physical examination** will be performed, i.e. only in case symptom is reported by the Participant, an assessment of the affected body system(s) will be performed.
- b **Vital signs** will include systolic and diastolic blood pressure and pulse rate while seated and at rest, and body temperature measured orally before vaccination. In addition, after an observation period of 30 minutes following vaccination pulse rate as well as blood pressure while seated and at rest will again be assessed.
- c A **urine** pregnancy test will be done prior to vaccination at Visit 7.

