A Data and Safety Monitoring Board (DSMB) will review the accrued safety data at Day 4 of all 15 sentinel participants. After favourable DSMB review randomization of the remaining 135 participants across all sites will be initiated.

The remaining 135 participants will be enrolled, screened and randomised to the three dose groups in the blinded part of the study. Participants will be observed for 30 minutes post vaccination on Day 1. All participants will be followed by e-Diary for 7 days post vaccination, starting on the day of vaccination. All participants will receive their second vaccination on Day 22 (Visit 3) and will be followed up on Day 36 (Visit 4), 14 days after the second vaccination.

PART B:

In Part B, participants will be followed up on Day 106 (Visit 5) and Day 208/Month 7 (Visit 6), 6 months after the second vaccination.

PART C (BOOSTER PHASE):

At Day 208/Month 7 (Visit 6), all participants who previously had received two study vaccinations will be invited to take part in the Booster Phase (Part C). Independently of the dose received during the primary immunization, participants will receive a booster dose (high dose) of VLA2001.

[figure not shown]
The Booster vaccination will also be offered to participants who have either had a confirmed COVID-19 disease or who have received a national COVID-19 vaccination.

The Booster vaccination will be administered at Visit 7. Participants will be asked to return to the study site for two follow-up visits, 14 days after the booster vaccination (visit 8) and 28 days after the booster vaccination (Visit 9).

6 months after the Booster vaccination, participants will be followed-up through a safety phone call. This telephone call is also the end of the study for the participants that consented to the booster part of the study.

Part A of the study will be completed when the last participant has completed Day 36 (14 days after the second vaccination). Part B of the study will be completed when the last participant has completed Day 208 (6 months after the second vaccination). The Booster Phase (Part C) will be completed when the last participant has completed the safety followup call 6 months (Visit 10) after the Booster vaccination.

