4.3 PER-PROTOCOL ANALYSIS SET (PPAS)

The Per-Protocol Analysis Set (PPAS) will consist of the FAS population including participants who have no major protocol deviations until the respective analysis time point (i.e. PPAS Day 36, PPAS Day 106 and PPAS Day 208). Participants who received an already licensed COVID-19 vaccine outside of the study or participants who received less than 2 vaccinations will be excluded.

These criteria for potential protocol violations are identified at the time of study planning. However, during the course of the trial unforeseen events may occur or new scientific knowledge may become available, therefore final decisions on all protocol violations will be made on a case by case decision in a data review meeting.

Immunogenicity analysis will be primarily carried out on the PPAS.

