In addition to the functional assays, samples are analysed for IgG against SARS-CoV-2 by a human anti-SARS-CoV-2 pre-spike IgG antibody ELISA (S-ELISA). In brief, the SARS-CoV-2 pre-spike recombinant antigen is adsorbed onto the 96-well microplate. Dilution series of human sera, standard and controls are added to microtitre plates coated with the SARS-CoV-2 pre-spike recombinant antigen. Presence of binding IgGs is detected with an anti-human IgG antibody conjugated to peroxidase, followed by addition of the peroxidase substrate. The optical density of the colored end product is proportional to the amount anti-SARS-CoV-2 pre-spike IgG antibodies present in the serum sample. Values below the quantitation limit of the ELISA (50.3 ELU/mL) and samples scored

as “negative” will be replaced by 25 ELU/mL. Also values above the quantitation limit (>15798 ELU/mL) will be replaced by 15798 ELU/mL.

Immunogenicity analysis will be presented for the respective PPAS and modified PPAS population. In addition analysis can also be presented for FAS population. Immunogenicity analysis may also be presented for “Unscheduled COVID-19 illness visit” that will be performed if a participant tests positive for COVID-19 during the study.

Immunogenicity analysis may also be presented stratified for MNA positive/negative at Visit 1. MNA result will be considered positive if result (ND50) \geq LLOQ, i.e. ≥ 62 . Otherwise if the result (ND50) $<$ LLOQ then MNA will be considered negative.

All secondary immunogenicity analysis for booster phase will be presented by primary treatment group (Low Dose/ Medium Dose/ High Dose) of participant and the tables will also be presented stratified by following factors: Received other COVID-19 vaccine any time during study / Not received other COVID-19 vaccine any time during study/ COVID-19 positive any time during study who did not receive other COVID-19 vaccine any time during study.

Immunogenicity analysis will also be presented for participants in PPAS and mPPAS who received a booster dose.

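### The booster immunogenicity strata count another COVID-19 vaccine or a positive test from any point in the study, so exposures after the blood samples can decide the stratum

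*SAP*

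**What the plan says.** SAP section 8 presents the secondary booster immunogenicity results by primary dose group and again by exposure strata. The first two strata are "Received other COVID-19 vaccine any time during study / Not received other COVID-19 vaccine any time during study"; the third is "COVID-19 positive any time during study who did not receive other COVID-19 vaccine any time during study". No date limit is attached to any of them.

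The schedule is clear. Protocol section 14 states that "a blood sample (10 ml) will be collected at Visit 7 (before vaccination), Visit 8 and Visit 9", and SAP 2.4 places the last of these "28 days after the booster vaccination (Visit 9". The study ends for boosted participants with the Visit 10 call at 6 months (SAP 2.4). Protocol 15.4.2 requires vaccines and their dates to be recorded until completion or termination. Protocol 22.3 keeps unplanned COVID-19 illness visits and adverse event assessment in place through the booster phase.

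Two analyses are relevant. SAP section 10 puts the third interim after all participants complete Visit 9. Protocol 16.5 adds: "Final analysis will be done when all participants have completed the last visit (visit 10".

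Elsewhere the SAP does bound exposure in time. The per-protocol set (SAP 4.3) looks at major deviations "until the respective analysis time point (i.e. PPAS Day 36, PPAS Day 106 and PPAS Day 208", and the modified set (SAP 4.4) applies the same limits to positive COVID-19 tests.

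**The concern.** A titre can be affected only by what happened before the blood was drawn. A stratum that also depends on later events mixes participants who had been exposed when sampled with participants who had not. It also takes out of the no-other-vaccine stratum people who belonged there at every sample. The likely effect is to blur the contrast between strata. The shift need not be random either: infection after the booster is plausibly related to how well the participant responded, so membership of the COVID-19-positive stratum could depend in part on the outcome being summarised.

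Protocol 8.5 says that "the effect of a booster dose will be studied in a population with different levels of pre-existing antibody levels", so readers will naturally take the stratified tables as describing the booster in people with and without other prior exposure. Under the present rule that interpretation would not be safe. The same participant, with the same titres, could also sit in different strata in two reports.

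**Working it through.** The plan gives no sample size, power or precision for these strata, so there is no figure to reproduce. The check sets the rule against the schedule and then illustrates the effect.

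**1. What the rule does, by date of first exposure**

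- Before Visit 7: exposed stratum, and all three samples follow the exposure. Correct.
- Between Visit 7 and Visit 9: exposed stratum, but the Visit 7 sample (and possibly Visit 8) precedes the exposure. Later samples carry the exposure's effect as well as the booster's.
- After Visit 9: exposed stratum, although all three samples precede the exposure.
- COVID-19 before Visit 7, other vaccine after Visit 9: moved from the COVID-19-positive to the other-vaccine stratum, on unchanged titres.

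**2. Length of the period after the last sample**

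Inputs: Visit 9 at 28 days (window 7 days either way) and Visit 10 at 6 months (window 14 days either way), from Protocol 22.3; 6 months taken as 182 days.

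- Nominal: 182 − 28 = 154 days.
- Shortest: (182 − 14) − (28 + 7) = 133 days. Longest: (182 + 14) − (28 − 7) = 175 days.
- Share of post-booster time: 154/182 = 85% (133/168 = 79% to 175/196 = 89%).
- Share of the whole period from Day 1, taking the booster at 21 days plus 8.5 months of 30.44 days, about 280 days: 154/(280 + 182) = 33%.

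These are shares of calendar time, not of exposures.

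**3. What the third interim can contain**

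Protocol 22.3 plans boosters for mid to end September 2021, with a 14-day window. Reading this as 15 to 30 September, boosters run from 1 September to 14 October. The earliest Visit 9 is then 1 September + 21 days = 22 September, and the latest 14 October + 35 days = 18 November, a spread of 57 days. The cut date is not stated. If it were the day of the last Visit 9, no participant would have more than 57 days between their own Visit 9 and the cut, and most would have fewer.

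**4. Size of the dilution (illustration only)**

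Let R be the true geometric mean ratio between participants exposed before the booster and those unexposed when sampled, and s the share of the exposed stratum exposed only after sampling. With an unexposed comparator, the ratio shown is R^(1 − s).

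- R = 5: s = 0.25, 0.50, 0.75 give 3.34, 2.24, 1.50.
- R = 2: the same shares give 1.68, 1.41, 1.19.

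If a fraction f is exposed before Visit 7 and a fraction g of the rest first after Visit 9, then s = (1 − f)g / [f + (1 − f)g]. With 80 boosted participants and f = g = 0.3, that is 24 exposed before and 16.8 after, so s = 16.8/40.8 = 41%, and R = 5 shows as 2.58. Letting f and g each take 0.1, 0.3 and 0.5, s runs from 9% to 82%, and R = 5 shows as 4.32 down to 1.34. R, f and g are assumptions; the documents give none of them.

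**The case against.** The strongest reply is that little depends on these tables. They are additional presentations of secondary endpoints, SAP 2.2 states no formal hypotheses, and about 80 boosted participants are expected. The booster titre tables are marked for the third interim, where the look-ahead is a matter of weeks. Protocol 15.4.2 bars other non-influenza vaccines for 30 days before and after a study dose, so few vaccinations should fall between Visits 7 and 9. Nor does the SAP say that the strata are meant to capture exposure before the booster.

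Most of this stands, and it limits the weight of the point. It does not remove it. The 30-day restriction ends at about the time of Visit 9, so it leaves later vaccination open, and it does not touch infections. The table index has no column for the final analysis, so it neither confirms nor rules out a repeat there. Whatever purpose was intended, exposure after a sample cannot inform that sample.

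A reader might infer more than the documents support:

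- **That another vaccine after Day 208 removes nobody from the per-protocol set.** The sentence in SAP 4.3 excluding recipients of a licensed COVID-19 vaccine carries no date, nor does the matching example in SAP 4.5, and final exclusions are decided case by case. Only the infection rule in SAP 4.4 is expressly tied to Days 36, 106 and 208.
- **That the per-protocol tables labelled for booster participants use the wrong cut-off.** SAP 8.3 assigns the booster-phase analysis to the booster ITT set. The per-protocol tables mirror the primary-series ones, including seroconversion, which SAP 8.2.2 measures from Day 1 for visits up to Day 208. They may show only primary-series visits in the boosted subset.
- **That the third secondary objective asks about pre-booster immunity.** It asks only for tolerability, safety and immunogenicity of a booster dose. The sentence in Protocol 8.5 about differing antibody levels follows one about response across the primary dose groups.

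**Conclusion.** The point holds. The rule in SAP 8 lets exposures after the blood samples, including after the last one, determine the stratum, and no other section corrects this. At the third interim the reach is from a participant's samples to an unstated data cut. If the tables are repeated at the final analysis, it extends over about 154 days after Visit 9 (133 to 175 with visit windows), and strata can change between reports on identical titres.

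The 85% share must not be read as the proportion misclassified: it is calendar time after the booster, falls to 33% when counted from Day 1, and applies in full only if the tables are rerun after Visit 10. How far the contrast would be diluted cannot be settled from the documents. The unstratified tables by primary dose group and the Day 36 primary endpoint are unaffected. This is a correction worth making to supplementary tables, not a threat to the main results.

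**What to change.** In SAP section 8:

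- Define both the other-vaccine and the COVID-19-positive factor as of the booster vaccination at Visit 7.
- For a first exposure between Visit 7 and Visit 9, leave samples taken after the exposure date out of the stratified tables and list them.
- Ignore exposures after Visit 9 for stratification.
- If the per-protocol tables for booster participants are meant to include Visits 7 to 9, say so, and extend the infection cut-off in SAP 4.4 to the visit being summarised. If they show only primary-series visits, no change is needed there.

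The cost is a short SAP revision and one date comparison per participant; vaccine dates are already recorded under Protocol 15.4.2, and COVID-19 test results are collected in the study. The drawback is that the exposed strata become smaller, in a group of only about 80 already split by three primary doses, so their confidence intervals will be wider. In return, each stratum describes exposure status before the booster and stays the same between the interim and final reports, apart from corrections to the data.

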#### Booster Phase:

At Visit 6 (Month 7), all participants who previously had received two study vaccinations will be asked for their consent to take part in the Booster Phase (Part C). Independently of the dose received during the primary immunization, participants will receive a booster dose (high dose) of VLA2001.

The Booster vaccination will also be offered to participants who have either had a confirmed COVID-19 disease or who have received a national COVID-19 vaccination.

The Booster vaccination will be administered at Visit 7. Visit 7 is expected to be performed in September 2021. This timing will translate to the booster dose being given to the participants at approximately 8 to 9 Months after completion of the primary immunization schedule.

Participants will be asked to return to the study site for two follow-up visits, 2 weeks after the booster vaccination (visit 8) and one month after the booster vaccination (Visit 9).

6 months after the Booster vaccination, participants will be followed-up through a safety phone call. This telephone call is also the end of the study for the participants that consented to the booster part of the study.

Additional safety data review by the DSMB will occur when necessary (ad-hoc) as defined in the DSMB Charter. A final review of the generated safety data will be performed by the DSMB once all participants have completed the clinical study.

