4.4 MODIFIED PER-PROTOCOL ANALYSIS SET (mPPAS)

Modified PPAS will include all participants from PPAS except those participants who were tested positive for COVID-19 anytime during study until the respective analysis timepoint (i.e. PPAS Day 36, PPAS Day 106 and PPAS Day 208) after first vaccination.

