4.7 ITT ANALYSIS SET: BOOSTER GROUP

The ITT for the booster group will include participants who received the booster dose with VLA2001.

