8.2.2 Proportion of Participants With Seroconversion in Terms of Neutralizing Antibodies

Seroconversion will be defined as ≥ 4 -fold increase in SARS-CoV-2-specific neutralizing antibody titre levels between Day 1 and post-vaccination sample collection timepoints. The fold increase is defined as a participant's post-Baseline titre at a visit divided by the baseline (Day 1) titre. The number and proportion of participants with seroconversion in terms of neutralizing antibodies on Day 8, Day 22, Day 36, Day 106 and Day 208, in participants negative for SARS-CoV-2 infection at Screening will be presented along with exact 95% Clopper-Pearson confidence interval (CI) for each dose group and overall. Differences between the dose groups will be assessed for significance using Fisher-Freeman-Halton exact test and p-values will be presented for this test. If overall group difference is statistically significant, i.e. p-value for Fisher-Freeman-Halton exact test is ≤ 0.05 , then multiplicity adjusted p-values (using Hochberg method) for pairwise group difference will be calculated for Fisher's exact test.

In addition, the number and proportion of participants with ≥ 2 -fold increase, ≥ 10 -fold increase and ≥ 20 -fold increase will also be presented for each post baseline visit.

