8.3 ANALYSIS OF SECONDARY IMMUNOGENICITY ENDPOINTS FOR THE BOOSTER PHASE

Analysis for booster phase will be presented for booster group ITT population.

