8.3.1 Geometric mean fold rise (GMFR) for SARS-CoV-2 Neutralizing Antibody Titres

Geometric mean fold rise (GMFR) of SARS-CoV-2 neutralizing antibody titres at Visit 8 and Visit 9 compared with pre-booster time point (Visit 7) and corresponding CI will be calculated using the same methodology as described for the primary immunogenicity endpoint.

The fold increase will be calculated as a participant's titre at a visit divided by the pre-booster time point (Visit 7) titre.

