8.3.3 Geometric mean titres (GMT) for SARS-CoV-2 Neutralizing Antibody Titres

GMTs along with corresponding 95% CI for neutralizing antibodies will be calculated using the same methodology as described for the primary immunogenicity endpoint. The results will be presented for Visit 7, Visit 8 and Visit 9.

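### The booster strata in SAP 8 nest rather than separate, so the six Visit 7-based booster tables name no stratum for participants with neither another COVID-19 vaccine nor a documented positive test

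*SAP*

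**What the plan says.** The protocol synopsis (Booster Phase) states that the booster will "also be offered to participants who have either had a confirmed COVID-19 disease or who have received a national COVID-19 vaccination"; SAP 2.4 repeats this. SAP 4.7 puts no exposure condition on the booster set: "The ITT for the booster group will include participants who received the booster dose with VLA2001". SAP 8.3 then assigns the booster endpoints to that set: "Analysis for booster phase will be presented for booster group ITT population". The SAP 13.2 index lists six such tables, 14.7.1.1 to 14.7.6.1, all for ITT (Booster).

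SAP 8 presents these results by primary dose group and also stratified by three factors. Stratum 1 is participants who received another COVID-19 vaccine during the study. Strata 2 and 3 are "Not received other COVID-19 vaccine any time during study/ COVID-19 positive any time during study who did not receive other COVID-19 vaccine", again at any time during the study.

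Fold rise in the booster analysis is a participant's "titre at a visit divided by the pre-booster time point (Visit 7) titre" (SAP 8.3.1). Booster GMTs and GMFRs with their intervals "will be calculated using the same methodology as described for the primary immunogenicity endpoint" (SAP 8.3.3, with the same instruction in 8.3.1, 8.3.4 and 8.3.6). That method is the ANOVA with dose group and site in SAP 8.1, with an unadjusted fallback if the log titres are not normally distributed.

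SAP 8 also plans tables for boosted members of the PPAS and mPPAS. The mPPAS removes participants who tested positive "until the respective analysis timepoint (i.e. PPAS Day 36, PPAS Day 106 and PPAS Day 208) after first vaccination" (SAP 4.4).

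**The concern.** Secondary objective 3 is the immunogenicity of a VLA2001 booster. Protocol 8.5 expects boosted participants to start from different antibody levels, and strata defined by prior exposure are the way to show what that does. The natural reference group is participants whose only documented exposure is VLA2001, and it is the one group without a name in the strata.

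Stratum 2 pools participants with and without a documented infection. If infection raises the Visit 7 titre, the pooled Visit 7 GMT is higher and the pooled fold rise may be lower than in participants without a documented infection. A reader who takes stratum 2 as VLA2001 only would misread both.

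A lesser point: the strata use exposure at any time during the study, so an infection after the booster can decide the stratum in which a pre-booster titre is shown. Visit 9 falls 21 to 35 days after Visit 7 (28 ± 7 days, Protocol 22.3). Protocol 15.4.2 disallows most other vaccines for 30 days either side of a study dose. At the third interim this is therefore mainly a matter of infections.

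**Working it through.** **1. Set check.** Cross other vaccine (yes/no) with documented positive (yes/no).

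| Cell | Stratum 1 | Stratum 2 | Stratum 3 |
|---|---|---|---|
| vaccine, positive | in | – | – |
| vaccine, not positive | in | – | – |
| no vaccine, positive | – | in | in |
| no vaccine, not positive | – | in | – |

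Strata 1 and 2 are disjoint and cover everyone. Stratum 3 is a proper subset of stratum 2. No stratum equals the last cell, called N below.

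**2. What can be recovered for N.**
- Tables 14.7.3.1 and 14.7.6.1 (4-fold counts): N is stratum 2 minus stratum 3, and an exact interval follows from the counts.
- Tables 14.7.1.1, 14.7.2.1, 14.7.4.1 and 14.7.5.1 (GMT, GMFR): under the unadjusted fallback, subtraction on the log scale works. Illustration with 40 in stratum 2, 8 in stratum 3, and assumed GMFRs of 20 in N and 2 in stratum 3. Stratum 2 shows 10^[(32 × log10 20 + 8 × log10 2)/40] = 12.6. Then 10^[(40 × log10 12.6 − 8 × log10 2)/32] returns 20. Under the site-adjusted ANOVA each stratum has its own fitted site effects and its own least-squares weighting, so neither estimate nor interval follows by subtraction.
- The booster listings in SAP 13.3 hold the individual values, so a rebuild is possible.

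**3. How close the boosted mPPAS tables come.** SAP 4.3 removes recipients of a licensed COVID-19 vaccine, and SAP 4.4 removes positives. Two limits remain.
- Fold increase there is the "post-Baseline titre at a visit divided by the baseline (Day 1) titre" (SAP 8.2.2; baseline also in 8.2.3 and 8.2.6), not a rise from Visit 7.
- The last listed infection cut-off is Day 208. Gap to Visit 7 from Protocol 10.1.3 (8 to 9 months after the Day 22 dose): 22 + 8 × 30.44 = Day 266 and 22 + 9 × 30.44 = Day 296; minus 208 gives 58 to 88 days. Gap for the last participant from the calendar: a Day 36 visit on 1 to 28 February 2021 plus 172 days is 23 July to 19 August. To 15 to 30 September (taking mid-month as the 15th) that is 27 to 69 days. Combined range 27 to 88 days. The ±14-day windows at Visits 6 and 7 widen it to 27 − 28 = −1 and 88 + 28 = 116 days.

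**4. Possible size of the mixing.** Let f be the share of stratum 2 with a documented positive, k the ratio of their Visit 7 titre to that of N, and b the share of that log difference still present at Visit 8. All three are assumptions.
- Visit 7 GMT, stratum 2 over N = k^f. With f = 0 or k = 1 it is 1.0; with f = 0.3 and k = 10 it is 10^0.3 = 2.0.
- GMFR, stratum 2 over N = k^(−f(1−b)). With b = 1 it is 1.0; with b = 0, f = 0.3 and k = 10 it is 10^(−0.3) = 0.5.

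**5. Size and precision of N.** With 80 boosted (SAP 2.5), an assumed share v = 0 to 0.6 vaccinated elsewhere and f = 0 to 0.3, n = 80(1 − v)(1 − f) runs from 80 to 22, or about 27 to 7 per primary dose group. The 95% CI multiplies and divides the GMT by 10^(t × SD/√n), with an assumed log10 SD of 0.4 to 0.6.

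| Display | n | df | CI factor |
|---|---|---|---|
| pooled over dose | 80 | 79 | 1.23–1.36 |
| pooled over dose | 22 | 21 | 1.50–1.85 |
| per dose group | 27 | 78 | 1.42–1.70 |
| per dose group | 7 | 18 | 2.1–3.0 |

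The per-dose rows use the variance pooled over three dose groups, as in the SAP's ANOVA, before site terms are deducted.

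**The case against.** The strongest reply is that nesting is not in itself an error. Strata 1 and 2 already partition the boosted participants, stratum 3 is a displayed subgroup of stratum 2, and the SAP nowhere says that strata must add up to the total. The label of stratum 2 makes no claim about infection. This stands: a reader might infer that the tables are miscounted or biased, and the documents do not support that.

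Second, table shells are not among the documents, and SAP 12.1 has output specifications written after the SAP is final. Stratum 2 may have been intended to exclude positives. That is possible, but stratum 3 spells out its vaccine condition while stratum 2 states no infection condition. SAP 12.2 relies on two programmers working independently from the written specifications, so the intention should be in the text.

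Third, the boosted mPPAS titre tables (14.3.1.4 and 14.3.4.4) may already give a near equivalent. SAP 8.2.1 speaks of every sampling visit, while SAP 8.2.4 lists days only up to 208; whether Visits 7 to 9 appear is not stated. If they do, a GMT close to that of N is planned for both assays. With complete data its ratio between visits is the GMFR point estimate, though without the paired interval. So it would go too far to say that the plan has nothing on an approximately unexposed group.

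Fourth, SAP 2.2 states that there are no formal hypotheses, and nothing is lost from the database. Both are true, and they limit how much this matters. A row built after the results are known is, however, post hoc; naming it now makes it prespecified.

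**Conclusion.** The concern holds in a limited form. As written, the third booster stratum is contained in the second. The six Visit 7-based tables on the booster ITT set therefore name no stratum for participants with neither another COVID-19 vaccine nor a documented positive test. Four of the six would report site-adjusted estimates that cannot be obtained for this group by subtraction. The mPPAS tables cover the gap only in part.

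This rests on the wording of SAP 8 and the table index, without the shells. No distortion is demonstrated: every share, titre ratio and SD used above is an assumption, and the resulting ranges (1.0 to 2.0 for the Visit 7 GMT, 0.5 to 1.0 for the GMFR) include no effect. A reader might infer that the booster results will be wrong or that information is missing. The documents show only that a useful planned summary is missing, for secondary and descriptive endpoints. It is a cheap improvement worth making.

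**What to change.** In SAP 8, split the stratum without another vaccine, using status before dosing at Visit 7, so that the strata become:

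- (a) other COVID-19 vaccine received;
- (b) no other vaccine, documented SARS-CoV-2 positive since first vaccination;
- (c) neither documented.

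Add a note that (c) may contain undetected infections, because testing under Protocol 15.2.5 is triggered by symptoms; it should not be labelled VLA2001 only. Flag Visit 8 and 9 samples taken after a later infection or vaccination.

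The mPPAS need not change, since extending it would not add a Visit 7-based table. If it is extended to Visits 7 to 9 for other reasons, its parent PPAS in SAP 4.3 must be extended as well. It would help to state whether tables 14.3.1.4 and 14.3.4.4 include Visits 7 to 9.

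The cost is SAP wording and one derived variable, with no new data. The price is smaller strata and wider intervals, most of all per primary dose group. A display of the strata pooled over primary dose is optional and would ease this.
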